****Rate the highest level of psychopathology. When in doubt, rate up and record the higher score.***

Global Assessment Functioning (GAF)

Consider psychological, social, and occupational functioning on a hypothetical continuum of mental health-illness. Do not include impairment in functioning due to physical (or environmental) limitations.

Indicate appropriate code for the **LOWEST level of functioning during the week of POOREST functioning in the past month.** (Use intermediate level when appropriate, i.e., 45, 68, 72).

Young Mania Rating Scale (YMRS)**General Instructions to the Clinician:**

The purpose of each item is to rate the severity of that abnormality in the patient. When several keys are given for a particular grade of severity, the presence of only one is required to qualify for that rating.

The keys provided are guides. One can ignore the keys if that is necessary to indicate severity, although this should be an exception rather than a rule.

Scoring between the points given (whole or half points) is possible and encouraged after experience with the scale is acquired; this is particularly useful when severity of a particular item in a patient does not follow the progression indicated by the keys.

Social Function Scale (SFS):

Used to measure the degree of functioning across several domains. Social engagement/withdrawal (amount of time to spend alone, the likelihood to initiate conversation) Interpersonal behavior (number of friends, engagement in a romantic relationship) Prosocial activities (participation in social activities e.g. visit friends, play sports). Additionally, it provides competency scores for items.

Brief Assessment of Cognition in Schizophrenia (BACS)

Instructions (Atkins et al. 2017):

Verbal Memory (Verbal Memory & Learning Domain): 7 min

Subjects hear a list of 15 words to remember. Words are presented by the App at a standard rate.

- Outcome measure: Total number of words recalled across 5 learning trials.

Digit Sequencing (Working Memory Domain): 5 min

Subjects are presented with randomly ordered auditory clusters of numbers (i.e., 936) with steadily increasing trial length. Items are presented by the App at a standard rate. Subjects are asked to report the numbers in order, from lowest to highest.

- Outcome measure: Number of trials with all items in the correct order.

Token Motor Task (Motor Function): 3 min

Subjects are presented with a virtual bowl and a supply of virtual tokens and asked to swipe a token from each side of the tablet with the index finger from each hand simultaneously and release them into the center container as rapidly as possible for 60 s.

- Outcome measure: Number of tokens correctly dragged into the container.

Semantic Fluency & Letter Fluency Tasks (Verbal Fluency Domain): 5 min

During Semantic Fluency, subjects are given 60 s to generate as many words as possible within the category: *Animals*. Subjects are asked to generate as many words as possible beginning with a given letter. Subjects are administered two trials using letters F and S.

- Outcome measures: Total words generated for each fluency task in addition to total scores from both tasks combined to produce the Verbal Fluency domain score.

Symbol Coding (Speed of Processing): 3 min

Subjects assign numbers to non-meaningful symbols with the use of a key that is provided. Numbers are entered on the digital keypad and appear in the location below the corresponding symbol. Following instructions and practice, subjects are given 90 s to complete as many items as possible.

- Outcome measure: Number items completed correctly within the 90 second test period.

Tower of London (Executive Functions/Reasoning and Problem Solving): 7 min

Subjects are shown 2 images presented on opposite sides of the tablet screen. Each image shows a different configuration of 3 colored balls arranged on 3 pegs. The subject is required to accurately determine total number of times the balls in one picture would have to be moved in order to make the arrangement of balls identical to that of the other, opposing picture, while employing the standard rules employed in tower tests (balls are moved one at a time and balls on top of other balls must be moved first).

[figure not shown]
- Outcome measure: Number of correct responses.

Self-Report tES Sensation Questionnaire

Given a participant after each tES session (2x20min), the questionnaire measures severity of sensations felt during the stimulation. Rated on a scale from 0 (none) to 4 (severe). In addition, the questionnaire has an open-ended question to allow participants to express any additional sensations felt during stimulation.

tDCS Montage:

Ensure to mark electrodes for stimulation and that correct settings are adjusted on tES device. A 30 second ramp should be set. All impedances should be checked before stimulation is delivered. Experimenters should remain blinded.

EEG Tasks Directions:

Resting State

For the next 5 minutes you will be asked to sit still and keep your eyes on a small white fixation cross at the center of the screen. Try to keep your eyes centered on that and try not to move excessively.

Reinforcement Learning Task

The game is divided into 4 sessions, each comprising 90 trials and lasting 10 minutes. The first session will be used as a practice session before scanning. The three other sessions will be performed when we record the EEG.

The word 'ready' will be displayed 10 seconds before the game starts.

In each trial you have to choose between the two symbols displayed on the screen, above and below the central cross. Your choice will be circled in red after a 4 second delay.

As an outcome of your choice, you may

- get nothing*
- gain +10*
- lose -10*

The two symbols displayed on a same screen are not equivalent in terms of outcome: with one you are more likely to get nothing than the other. Each symbol has its own meaning, regardless of where and when it is displayed.

The aim of the game is to win as much money as possible.

BART and Go/No Go:

These assessments will be conducted for all participants: These tests are run via **ePRIME**.

Set-Up:

BART

1. Connect eRPIME computer
2. Move the head and chin rest to be **75 cm from the monitor** (marked with tape on the floor)
3. Attach keyboard to computer and place on desk
4. Use alcohol wipe to clean:
 - a. Forehead and chin rest
 - b. Keyboard
5. Open up “**BART_2**” instructions
 - a. You will use this to describe the tasks to the participant
6. Open up “**BART_2**”
 - a. Load in program

Go/No Go

7. Connect eRPIME computer
8. Move the head and chin rest to be **75 cm from the monitor** (marked with tape on the floor)
9. Attach keyboard to computer and place on desk
10. Use alcohol wipe to clean:
 - a. Forehead and chin rest
 - b. Keyboard
11. Open up “**Go/No Go**” instructions
 - a. You will use this to describe the tasks to the participant

12. Open up “Go/No Go”

a. Load in program

DATABASE Quality Assurance and Analysis

The clinical database will be reviewed and checked for omissions, apparent errors, and values requiring further clarification using computerized and manual procedures.

Description of Study Endpoints

Primary Endpoint

Change from baseline to day 5, 1 month and 3 month in clinical measures (PANSS, ASRM) and hospitalizations after 1 week of tES.

Secondary Endpoints

Change from baseline to day 5, 1 month and 3 month in GAF, SFS total score after 1 week of tES. Change from baseline to day 5 and 1 month in MADRS, PANSS, BIS after 1 week of tES. Change from baseline to day 5 and 1 month in voltage and peak frequency for reinforcement learning task measures after 1 week of tES. Change from baseline to day 5, 1 month and 3 month in cognition scores after 1 week of tES. Change from baseline to day 5, 1 month and 3 month in behavioral tasks (BART & Go/No Go) scores after 1 week of tES.

Safety and Tolerability Endpoint

A self-rated questionnaire related to sensations of tES is given to participants after each stimulation.

General Statistical Considerations

All collected study data will be collected on Redcap and processed using R and Matlab software. Descriptive statistics (n, mean, standard deviation, median, minimum and maximum) will be calculated by treatment group and sham group for continuous variables.

Primary Analyses

Primary Analysis of the primary, secondary, and additional efficacy endpoints: Mixed Model Repeated Measures analysis (MMRM)/non- parametric methods will be used to compare using within group differences as well as to determine the difference between the two treatment groups on the primary, secondary and safety endpoints depending on the distribution of the data.

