**Causal Lesion Network Guided Treatment of Bipolar Mania
With Transcranial Electrical Stimulation**

NCT #: NCT05445466

June 23, 2025

Protocol Number:	2022P000295
Title:	Causal Lesion Network Guided Treatment of Bipolar Mania With Transcranial Electrical Stimulation
Design:	Double blind, design with baseline, day 5, 1 month and 3 month follow up visits during which transcranial electrical stimulation (tES) was delivered to the right orbital frontal cortex (rOFC) from baseline to day 5 each day (5 days) twice a day for 20 mins. Participants were randomly assigned to either cathodal transcranial direct current (tDCS), 10hz or personalized transcranial alternating current (tACS) conditions to test the effectiveness and feasibility of stimulating the rOFC using a novel targeting methodology consisting of a lesion network guided brain target linked to mania symptoms.
Objectives:	Evaluate the effectiveness and safety of transcranial electrical stimulation for improving the mania symptoms
Enrollment:	14 Individuals
Clinical Sites:	Beth Israel Deaconess Medical Center, Boston, MA
Patient Population:	Male or female outpatients 18-65 years of age patient's diagnosis with either bipolar or schizoaffective disorder, or history of mania as defined by DSM-5 or DSM-IV-TR criteria
Primary and Secondary Outcomes:	Primary Outcomes: Young Mania Rating Scale (YMRS); Altman Self-Rated Mania Scale (ASRM); Average Hospitalizations Secondary Outcomes: Balloon Analogue Risk Task (BART); The Go/No Go Task; Reinforcement Learning Task (RLT); Social Functioning Scale (SFS); Positive and Negative Syndrome Scale (PANSS); Global Assessment of Functioning (GAF); Barret Impulsiveness Scale (BIS); Resting State EEG; Brief Assessment of Cognition (BAC); Montgomery-Asberg Depression Rating Scale (MADRS)
Inclusion Criteria:	
 1. Aged 18-65 years of age 2. Proficient in English 3. Able to give informed consent 4. Meet diagnostic criteria for bipolar disorder or schizoaffective disorder, bipolar type as verified by the SCID 5. History of mania (>1 lifetime episode) 6. Experiencing mild to moderate symptoms of mania 7. No changes to mood stabilizing medications for a period of 2 weeks prior to participation 8. Has not recently participated in tES/TMS treatments

	In addition to the criteria above, participants for this stimulation procedure will be included if they have a history of mania and may or may not be experiencing symptoms currently.

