Study Rationale: Mania is a core symptom of bipolar disorder involving periods of euphoria, delusions, and overactivity. Mania occurs in multiple medical and psychiatric illnesses and can be refractory to existing treatments. Two recent studies using brain lesion mapping of psychiatrically healthy individuals presenting with mania identified causal locations in the brain, including the orbitofrontal cortex (OFC), dorsolateral prefrontal cortex (DLPFC), and inferior temporal gyrus (ITG), that were associated with new onset mania symptoms. Moreover, these identified brain regions have also been implicated in bipolar mania with specific disruption in network communication between the amygdala and ventro-lateral prefrontal cortex. The OFC is of particular interest because it is a brain structure that is associated with inhibitory control, risk-taking behavior, and reward, which are major behavioral components of mania. Thus, the association between OFC with mania symptoms, inhibitory control, risk-taking behavior and reward suggests that this region could be targeted using noninvasive brain stimulation. While several studies have non-invasively targeted the DLPFC for mania, no study to date has non-invasively stimulated the OFC with either transcranial direct current stimulation (tDCS) or alternating current (tACS) in bipolar disorder and examined its effects on mania, inhibitory control, or risk-taking behavior. However, a study in healthy volunteers showed that cathodal stimulation to the OFC enhanced inhibitory control and decreased risk-taking behavior. Recently, research have showed that targeting the OFC with tACS, personalized to the individual's intrinsic beta-gamma frequency of the reward network, that individuals showed rapid, reversible, frequency-specific modulation of reward-guided choice behavior and learning. Here we aim to answer the question of whether noninvasive brain stimulation when optimally targeted and personalized to an individual's beta-gamma frequency to the OFC can improve emotional cognitive processing and mania symptoms compared to tDCS or sham targeting. The knowledge gained from this study will provide a marker for clinical response and allow personalized treatment for patients with bipolar disorder.

Study Protocol:

Study Timeline

Study Visit Timeline	Visit 1	Visit 2	Visit 3	Visit 4	Visit 5	Visit 6 (1-month follow up)	Visit 7 (3-month follow up)
Consent	X						
Clinical Evaluation	X				X	X	X

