Tasks/Cognition Testing	X				X	X	X
EEG	X				X	X	X
tES	X	X	X	X	X		
Sensation Questionnaire	X	X	X	X	X		
Self-Reports	X				X	X	X

Study Visits and Details:

Participants will complete baseline clinical, neuropsychological, behavioral tasks and neurophysiological assessments (day 0), short-term follow-up (day 5) and long-term follow-up (1 & 3 month).

Pre-Screening

Subjects will be prescreened. If the subject appears to qualify for the study, they will be invited in for a screening and a baseline visit.

Screening and Baseline Procedures (approximately 3-4 hours)

Screening and baseline procedures will be conducted in the Massachusetts Mental Health Center (MMHC)/ Beth Israel Deaconess Medical Center (BIDMC) in Boston, MA. The urine toxicology screen and pregnancy test will be completed at MMHC or within BIDMC.

- Eligibility pre-screen will include a telephone pre-screening questionnaire that will assess basic inclusion and exclusion criteria.

- Eligibility screening will include a screening questionnaire that will assess more details related to inclusion and exclusion criteria and will be conducted in-person during the clinical diagnostic session (i.e., the first visit to the laboratory).

- Informed consent will be obtained

- Urine toxicology screen

- Urine pregnancy testing for females of childbearing age

Subjects will be informed that if they do not pass the urine toxicology screen (other than prescribed medication), they will be withdrawn from the study and will not receive compensation for the initial visit. This will be made clear in the pre-screening questionnaire.

- tES screening questions for tES participation

- Demographics: Subjects will be asked to provide standard demographic information (age, sex, race/ethnicity, level of education, cohabitation status) using forms employed in previous studies.

- Psychiatric, medical, substance use history and medication review

- Signing a release to allow for access to recent psychiatric records, if confirmation of medications or psychiatric history is necessary

OBJECTIVES

Primary Objective

The primary objective of this study is to evaluate the effectiveness of tES for improving the mania symptoms (YMRS, ASRM and hospitalizations).

Secondary Objectives

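### The day-5 GAF change is rated over a past-month window that lies mostly before stimulation, so it can barely register benefit; report it descriptively and do not test it

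*Combined protocol and SAP*

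**What the plan says.** - **Rating rule.** Under Clinical Assessments, the GAF entry tells raters to code the "LOWEST level of functioning during the week of POOREST functioning in the past month". The same rule applies at every visit, and nothing replaces it with a shorter period at Visit 5.
- **Endpoint.** Secondary Endpoints lists "Change from baseline to day 5, 1 month and 3 month in GAF, SFS total score after 1 week of tES".
- **Analysis.** Primary Analyses applies mixed models or non-parametric methods to "compare using within group differences as well as to determine the difference between the two treatment groups on the primary, secondary and safety endpoints". GAF at day 5 is not exempted.
- **Timing.** The synopsis (Design) has stimulation running "from baseline to day 5 each day (5 days) twice a day for 20 mins". Study Visits and Details puts the baseline assessments at day 0 and the short-term follow-up at day 5.
- **Contrast.** The PANSS, ASRM and MADRS entries each use a look-back of one week.

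**The concern.** The GAF score as defined is a minimum over a month. At day 5 that month is almost the same month that was rated at baseline. An improvement that begins with stimulation adds a few better days to the window, but better days do not raise a minimum. The score rises mainly when an old bad period falls out of the far end of the window, and that happens with or without treatment.

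Two readings of the results are at risk. A null day-5 difference between arms could be taken as no early effect on functioning, although the measure could hardly have shown one. A within-group rise at day 5 could be taken as early benefit, although a bad period before baseline may simply have left the window. Global functioning is a named secondary objective, so either misreading would reach the report.

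**Working it through.** The documents give no sample-size, power or SD figure for GAF, so there is no stated number to reproduce. Parts 1 and 2 need only day counts. Parts 3 to 5 rest on stated assumptions.

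**Inputs.** Interval from baseline to day 5: s = 5 days from the day-0 and day-5 labels, or 4 if Visit 1 counts as day 1. Look-back M: one month, not given in days; assumed 30, range 28-31.

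**1. Days already rated at baseline** = (M - s)/M.
- M = 30: 25/30 = 83% (s = 5); 26/30 = 87% (s = 4).
- Extremes over M = 28-31: 23/28 = 82% and 27/31 = 87%.

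Only 4-5 days follow baseline, so the day-5 window holds no complete post-baseline week.

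**2. Possible worst weeks still in the window.** An M-day window holds M - 6 seven-day weeks. After s days, M - 6 - s of the baseline weeks remain.

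| M | s = 5 | s = 4 |
|---|---|---|
| 28 | 17/22 = 77% | 18/22 = 82% |
| 30 | 19/24 = 79% | 20/24 = 83% |
| 31 | 20/25 = 80% | 21/25 = 84% |

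These are probabilities only if every week is equally likely to be the worst. If the worst week tends to be recent, it is even less likely to drop out by day 5.

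**3. Share of a true improvement that day-5 GAF shows.** Simulation under assumed conditions: stationary daily functioning with SD 1, day-to-day correlation 0 to 0.95, 40,000 participants per setting, and an immediate sustained gain of 0.5, 1 or 2 SD from the first post-baseline day. GAF is scored as the minimum in the worst week, or as the worst day as a check. Mean day-5 change divided by true gain:
- M = 30: 0.019-0.145
- M = 28: 0.021-0.152
- M = 31: 0.019-0.139
- M = 30 with independent rater error of SD 0.5 at both visits: 0.019-0.152

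This gives about 2-15%. A separate simulation used 20,000 participants, M = 30, s = 5, within-person SD 5, and the worst-week mean or the worst day. A true gain of 10 points moved day-5 GAF by 0.40-0.52 points, and a gain of 20 points by 0.41-0.53, which is 2-5% of the gain. With follow-up at 30 and 90 days the same rule showed essentially all of it.

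**4. Recovery already under way, no treatment effect.** If functioning improves along a straight line through baseline and day 5, moving the window by s days raises the expected minimum by s times the daily slope. Assume recovery of 1-3 SD per 30 days:
- smallest: 4 × 1/30 = 0.13 SD
- largest: 5 × 3/30 = 0.50 SD

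This rise appears with no effect of stimulation.

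**5. Dilution if visits are averaged.** The plan does not say whether a GAF effect will be averaged over visits. With equal weights, a constant effect fully shown at 1 and 3 months, and 2-15% of it shown at day 5, the average shows (0.02 + 1 + 1)/3 = 67% to (0.15 + 1 + 1)/3 = 72% of the effect.

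**The case against.** **The simulations are assumed.** This is true. The overlap in parts 1 and 2 does not depend on them, and the percentage of an improvement shown should be read as an order of magnitude.

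**The direction of any distortion is not fixed.** This stands. A reader might infer that day-5 GAF is biased towards showing worsening, or that its expected change without an effect is zero. Both need stable functioning before baseline, which the documents do not establish. The synopsis asks for mild to moderate manic symptoms and then also admits people with past mania whether or not they have symptoms at entry. Some may be recovering, and part 4 shows that their scores would then drift upwards. Randomisation means that neither pattern favours an arm.

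**Counting participants whose score rises is unreliable.** This also stands. With error-free rating, 12-21% rise at day 5 when there is no effect. With rater error of SD 0.5 at each visit, about 50% do. Such counts are not used here.

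**The 1-month GAF has the same problem.** A reader might infer this and ask for a minimum interval to Visit 6. The documents do not support it. They do not say whether the month to Visit 6 runs from Visit 1 or from the end of stimulation, and overlap needs a visit interval shorter than the look-back. Moving Visit 6 would also shift every other assessment at that visit.

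**Dropping a listed time point after data exist is a post hoc change.** The synopsis says that "transcranial electrical stimulation (tES) was delivered to the right orbital frontal cortex (rOFC) from baseline to day 5", in the past tense, so data may exist. The objection is met by disclosing the change and still reporting the day-5 values.

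**The consequence is small.** With 14 participants, a null result on any secondary scale is weak evidence. That limits the importance of the point but does not remove it.

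**Conclusion.** The point holds and is minor. As written, the plan tests a day-5 GAF change that can register little of any early benefit: 79-83% of the possible worst weeks at baseline are still in the window (77-84% for months of 28-31 days), and about 2-15% of an immediate improvement is shown. The first figure rests on the month length and a 4-5 day interval. The second also assumes stationary functioning before baseline and an immediate, sustained gain.

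The effect on a between-arm comparison is lost sensitivity. A within-group change is hard to interpret in either direction, depending on whether participants are stable or recovering at entry. The documents do not show that the GAF rule is wrong in itself, that day-5 GAF cannot change at all, or that the 1-month and 3-month GAF comparisons are compromised.

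**What to change.** 1. In Secondary Endpoints, split the shared GAF and SFS line. GAF change is tested at 1 and 3 months; SFS total score keeps day 5, 1 month and 3 months.
2. Add: *GAF at day 5 is reported descriptively by arm, because its past-month window is mostly pre-stimulation; it is not tested and does not enter any GAF treatment effect averaged over visits.*
3. If data have already been collected, disclose this as a change to the plan and still report the day-5 values.
4. Leave the Visit 6 schedule as it is, and report each participant's actual interval from Visit 1 to Visit 6 so that any overlap with the baseline window can be seen.

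The cost is a few lines of wording and one fewer tested GAF time point. No assessment is added, moved or dropped, and the descriptive report keeps any day-5 change visible, including a worsening.

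### Within-condition gains on the repeated cognitive and behavioural tests cannot be separated from practice, so tES conclusions on them should rest on between-condition change

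*Combined protocol and SAP*

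**What the plan says.** **Schedule.** The Study Timeline table places tasks and cognition testing at Visits 1, 5, 6 and 7, which Study Visits and Details gives as day 0, day 5, 1 month and 3 months. The first retest therefore comes within days.

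**Endpoints.** Secondary Endpoints lists "Change from baseline to day 5, 1 month and 3 month in cognition scores after 1 week of tES", and the same three times for BART and Go/No Go. The reinforcement learning endpoint is narrower: "Change from baseline to day 5 and 1 month in voltage and peak frequency for reinforcement learning task measures after 1 week of tES".

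**Test material.**
- Letter fluency (BACS section): "Subjects are administered two trials using letters F and S". Semantic fluency names a single category, animals.
- Verbal memory: "Subjects hear a list of 15 words to remember". Nothing is said about which list is used at later visits.
- BART and Go/No Go: the set-up steps each name one program to load.
- Reinforcement learning (EEG Tasks Directions): participants are told that "Each symbol has its own meaning, regardless of where and when it is displayed".
- Alternate forms, counterbalancing of forms or an allowance for practice are not described for any test.

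**Conditions and analysis.** Enrolment is "14 Individuals". The synopsis states: "Participants were randomly assigned to either cathodal transcranial direct current (tDCS), 10hz or personalized transcranial alternating current (tACS) conditions". No sham appears in that list, although descriptive statistics "will be calculated by treatment group and sham group for continuous variables" and the Study Rationale also speaks of a sham comparison. Primary Analyses applies MMRM or non-parametric methods both to change within a group and to the difference between two treatment groups, for primary, secondary and safety endpoints. The Statistical Methodology row of the synopsis likewise names both kinds of comparison.

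**The concern.** People tend to do better on a performance test the second time, and more so when the prompts are the same. Someone asked for words beginning with F and S, and for animals, at baseline gets those prompts again at day 5. A before-after comparison within one condition adds any such gain to any effect of stimulation. An untreated or sham group would show the size of the practice gain, but none is among the listed randomised conditions.

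What is at stake is the reading of the secondary endpoints. The Study Rationale asks whether stimulation improves emotional cognitive processing, and the objectives use BART and Go/No Go to judge whether the right orbitofrontal cortex was effectively targeted. A significant within-condition gain on these tests could be reported as evidence on either question when stimulation had done nothing.

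**Working it through.** The documents give no alpha, power, SD, effect size, practice gain or retest correlation, so there is no figure of theirs to reproduce. What follows is an illustration.

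**Inputs from the documents.** Total n = 14; analysis of change from baseline; within-group and between-group contrasts. No allocation ratio is given.

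**Assumptions.** Two-sided alpha 0.05; practice gain g of 0.2 to 0.5 baseline SD; correlation r of 0.6 to 0.8 between baseline and retest; groups of 7 (two groups) or about 5 (three groups, 5/5/4). A paired t-test at one visit stands in for the within-group contrast.

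**Step 1: standardised change.** With no tES effect and equal SDs, dz = g / sqrt(2(1 - r)). At g = 0.3:
- r = 0.6: 0.3 / sqrt(0.8) = 0.34
- r = 0.7: 0.3 / sqrt(0.6) = 0.39
- r = 0.8: 0.3 / sqrt(0.4) = 0.47

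**Step 2: chance of a significant within-group result with no tES effect.** This is the two-sided rejection probability of a noncentral t with n - 1 degrees of freedom and noncentrality dz × sqrt(n). Ranges run over r = 0.6 to 0.8.

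| n in the test | g = 0.2 | g = 0.3 | g = 0.5 |
|---|---|---|---|
| 5 | 6.8-8.6% | 9.0-13.1% | 16.3-27.6% |
| 7 | 7.9-11.0% | 11.7-18.6% | 24.0-42.0% |
| 14 (pooled) | 12.1-19.5% | 21.4-37.6% | 49.1-78.1% |

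At g = 0.1 the pooled figure is 6.7-8.5%, so a small practice gain does little harm.

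**Step 3: the between-condition contrast on the same kind of data.** In 20,000 simulated trials with r = 0.7 and the same practice gain in every condition, the error rates were:
- 7 against 7, t-test on change: 4.9% (g = 0.2) and 5.1% (g = 0.5)
- 5/5/4, one-way F test on change: 4.9% and 4.8%
- within-group test on all 14: 14% and 61%

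Practice common to randomised conditions cancels on average.

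**Step 4: the price in precision.** At r = 0.7 the SD of change is sqrt(0.6) = 0.775 baseline SD. For 7 against 7 the standard error of the difference in change is 0.775 × sqrt(2/7) = 0.414 SD. With t = 2.179 on 12 degrees of freedom, the 95% interval is about ±0.90 SD. The contrast is valid but wide.

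**Step 5: reinforcement learning exposure.** One administration is 4 × 90 = 360 trials, of which 3 × 90 = 270 are recorded with EEG. How far this carries into day 5 depends on whether the symbols are the same, which is not stated.

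**The case against.** The best defence is that the plan already includes the contrast that is protected from practice. Between-group comparison is named in both the synopsis and Primary Analyses, and it keeps its error rate. That stands, and it confines the concern to within-condition inference. It does not remove it, because the plan gives within-group change the same standing.

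Three stronger readings are tempting, and the documents do not support them.

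- *The reinforcement learning symbols are reused, so participants begin day 5 already knowing the answers and the task measures memory.* A reader might infer this from the instruction that a symbol's meaning does not depend on when it is shown. That sentence comes just after a description of symbols placed above and below a central cross. It reads naturally as a statement about position and trial order within one game. Nothing says what symbols are used at later visits, or whether the practice session is repeated. The endpoint is also an EEG measure at day 5 and 1 month only, and the documents do not show which way familiarity would move it.
- *All test material is fixed.* Only the fluency prompts are. A 15-word list describes a test format, delivered by an app whose forms cannot be judged from here. For the other tests the supportable statement is that alternate forms are not specified.
- *Four in ten null trials would show an effect.* The 38% figure pools all 14 participants and takes the highest correlation considered. Within a single condition of 5 to 7 people the corresponding range is 9-19%.

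It is also fair to say that these are secondary endpoints. The mania scales and hospitalisations involve no task practice.

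**Conclusion.** The concern holds for within-condition change on the BAC, BART and Go/No Go. It rests on four facts in the text: four scheduled administrations, fixed fluency prompts with no alternate forms or practice adjustment for any test, within-group change as a planned analysis, and no sham among the listed randomised conditions. It does not depend on symbol reuse, since familiarity with a task can raise retest scores even on new material.

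At an assumed practice gain of 0.3 SD the within-condition false-positive rate is roughly two to four times nominal. It is higher if conditions are pooled and close to nominal if practice gains are very small. For the reinforcement learning measures the same caution applies to within-condition change, but the documents establish neither carry-over of learned symbols nor its effect on the EEG.

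**What to change.** **Analysis (applies to data already collected).** In Primary Analyses, state that within-condition change on the BAC, BART, Go/No Go and reinforcement learning measures is descriptive only. State that any tES conclusion on these measures rests on between-condition differences in change from baseline at the same visit. Name the conditions compared and say whether a sham group exists. If all conditions are active, say that the contrast shows relative effects only.

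**Test material.** Record which form or symbol set was used at each visit. For testing still to be done, use alternate fluency letters and categories. Do the same for word lists and reinforcement learning symbol sets wherever the same ones would otherwise be reused, with order counterbalanced across participants. The synopsis describes delivery and randomisation in the past tense, so this part may no longer be possible. Only if the records show that symbols were reused should the day 5 and 1 month reinforcement learning results be described as reflecting retention.

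**Cost.** The analysis change is a few sentences. Alternate forms need a stimulus list and a form order, with no added testing time. They bring some form-to-form noise and do not remove general task familiarity, so the analysis change is needed either way. The main price is the wide between-condition interval with 14 participants, which should be reported as it is.
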